2.8. Imputation Rules for Missing AE Date/Time of Onset/Resolution

Partial AE onset dates will be imputed as follows:

- If the onset date of an adverse event is missing day only, it will be set to:
 - First day of the month that the AE occurred, if month/year of the onset of AE is different than the month/year of the study treatment
 - The day of study treatment, if the month/year of the onset of AE is the same as month/year of the study treatment start date and month/year of the AE resolution date is different
 - The day of study treatment or day of AE resolution date, whichever is earliest, if month/year of the onset of AE and month/year of the study treatment start date and month/year of the AE resolution date are the same
- If the onset date of an AE is missing both day and month, it will be set to the earliest of:
 - January 1 of the year of onset, as long as this date is on or after the study treatment start date
 - Month and day of the study treatment start date, if this date is the same year that the AE occurred
 - Last day of the year if the year of the AE onset is prior to the year of the study treatment start date,
 - The AE resolution date.
- Completely missing onset dates will not be imputed.

Partial AE resolution dates not marked as ongoing will be imputed as follows:

- If the resolution date of an AE is missing day only, it will be set to the earliest of the last day of the month of occurrence of resolution or the day of the date of death, if the death occurred in that month.
- If the resolution date of an AE is missing both day and month, it will be set to the earliest of December 31 of the year or the day and month of the date of death, if the death occurred in that year.
- Completely missing resolution dates will not be imputed.

3. INTERIM ANALYSIS AND DATA MONITORING COMMITTEE REVIEW

No interim analysis is planned for the study primary endpoint. The primary endpoint analysis will be performed after all randomized patients have completed 12 months of maintenance treatment, have disease progression, died, or have been discontinued/withdrawn from study treatment by this time point.

One interim analysis, at the time of primary endpoint analysis, and a final analysis, is to be conducted for PFS. Obrien-Fleming alpha spending function will be used to control overall 2-sided alpha at 0.05.

Final analysis will occur at the end of study which is 36 months from the date of randomization of the last patient, disease progressed, died, or withdrawal of consent, whichever occurs first.

An Independent Data Monitoring Committee, consisting of at least 2 clinicians and 1 statistician, is to be established to review safety data before the primary analysis of the MRD negativity rate, which is to be conducted by the sponsor. The Independent Data Monitoring Committee is to start their review after the first 100 patients have been treated for at least 4 cycles or discontinued and subsequently perform their review every 6 months. Details were provided in a separate Independent Data Monitoring Committee charter.

4. SUBJECT INFORMATION

The number of subjects in each analysis set will be summarized by treatment group, and overall. A listing will be provided with subjects' demographic information.

4.1. Demographics and Baseline Characteristics

Table 2 presents a list of the demographic variables that will be summarized by treatment group and overall for the FAS.

Continuous Variables:	Summary Type
Age (years)	Descriptive statistics (N, mean,
Height (cm)	standard deviation [SD], median and range [minimum and
Baseline body surface area (BSA) (m ²)	maximum]).
Categorical Variables	
Age (<65, 65-70, ≥70 years)	

Table 2: Demographic Variables

Sex (male, female, undifferentiated)	Frequency distribution with the
Race ^a (American Indian or Alaska Native, Asian, Black or African	number and percentage of subjects
American, Native Hawaiian or other Pacific Islander, White, Other)	in each category.
Ethnicity (Hispanic or Latino, not Hispanic or Latino)	
Baseline weight ($\leq 70, >70$ kg)	

Table presents a list of the baseline characteristics variables that will be summarized by treatment group and overall.

Table 3: Baseline Characteristics Variables

Continuous Variables	Summary Type	
Time from diagnosis of multiple myeloma to date of randomization	Descriptive statistics (N, mean,	
(months)	standard deviation [SD], median	
Time from the ASCT day to the randomization (months)	and range [minimum and	
Number of induction cycles	maximum]).	
Received consolidation treatment? (Yes/No)		
Categorical Variables		
Presence of diffuse myeloma-related osteopenia at baseline		
Baseline number of lytic bone lesions (none, 1-3, 4-10, >10)		
Number of extramedullary plasmacytomas $(0, \geq 1)$		
Baseline ECOG (0, 1, 2, >2)		
ISS stage at diagnosis (I, II, III)		
Medical history collected at baseline or screening visit (by system organ		
class, preferred term)	Frequency distribution with the	
Cytogenetic risk at screening by del(17p), t(4; 14), t(14; 16) (standard risk,	number and percentage of subjects	
high risk)	in each category.	
Revised cytogenetic risk at screening by del(17p), t(4; 14), t(14; 16), t(14;		
20), gain/amp1q21 (standard risk, high risk)		
Cytogenetic risk at MM diagnosis by del(17p), t(4; 14), t(14; 16) (standard		
risk, high risk)		
Revised cytogenetic risk at MM diagnosis by del(17p), t(4; 14), t(14; 16),		
t(14; 20), gain/amp1q21 (standard risk, high risk)		

4.2. Disposition Information

For screen failed subjects, reasons for screen failures will be listed.

The number and percentage of subjects in the following disposition categories will be summarized throughout the study by treatment group and overall:

- Subjects randomized
- Subjects randomized and received at least one dose of study treatment
- Subjects randomized and not treated by study treatment
- Subjects who completed all randomized study treatment(s)
- Subjects who discontinued all randomized study treatment(s)
- Subjects who discontinued any randomized study treatment

- Subjects who completed lenalidomide treatment
- Subjects who discontinued lenalidomide treatment
- Reasons for discontinuation of lenalidomide treatment
- Subjects who completed daratumumab treatment
- Subjects who discontinued daratumumab treatment
- Reasons for discontinuation of daratumumab treatment
- Subjects completed the study
- Subjects who discontinued study prematurely
- Reasons for study discontinuation

Duration of follow-up time in months will be summarized descriptively as well as reverse Kaplan-Meier method.

A listing of subjects will be provided for the following categories:

- Study disposition
- Treatment disposition
- Randomization information
- Subjects who were randomized but were not treated.

4.3. Extent of Exposure

Extent of exposure to study treatments will be summarized and presented based on the safety analysis set.

The dose intensity, which is defined as the sum of total dose administered in all cycles divided by the number of treatment cycles, will be calculated for each study treatment and summarized accordingly.

The relative dose intensity (%) defined as the ratio of total dose actually received and total planned dose (planned dose level times the number of administered injections/medications) will be calculated for each study treatment and summarized by treatment group using descriptive statistics. The planned dose for daratumumab is 1800 mg and 10 mg for lenalidomide per administration.

The number and percentage of subjects treated within each cycle will be summarized by treatment group. The total number of treatment cycles received for each subject will be summarized by frequency and descriptive statistics. The total number of daratumumab administrations will be summarized by descriptive statistics.

Duration of study treatment, defined as the number of months from the date of the first administration of study treatment to the date of the last administration of study treatment, will be summarized.

The number of subjects with treatment cycle delay, dose delay, dose skipped and dose adjusted for each study treatment will be summarized, respectively. The reasons (AE or other) for treatment cycle delay, dose skipped and dose adjusted for each study treatment will also be summarized.

4.4. **Protocol Deviations**

In general, the following list of major protocol deviations may have the potential to impact subjects' rights, safety or well-being, or the integrity and/or result of the clinical study. Subjects with major protocol deviations will be identified prior to database lock and the subjects with major protocol deviations will be summarized by category for the FAS including:

- Entered study but did not satisfy inclusion or exclusion criteria
- Developed withdrawal criteria but not withdrawn
- Received wrong treatment or incorrect dose
- Received a disallowed concomitant treatment
- Efficacy assessment deviation
- Safety assessment deviation, whether it is COVID-19 related
- Other

A listing of all major protocol deviations including COVID-19 will be provided by displaying subject ID, type of deviation, and reasons for deviation.

Subjects with protocol deviations related to COVID-19 will be summarized. A listing of subjects with minor protocol deviations related to COVID-19 will be provided.

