6. DOSAGE AND ADMINISTRATION

6.1. Daratumumab and Lenalidomide Dosing and Supply

Maintenance treatment regimens in this study comprise of SC daratumumab in combination with lenalidomide or lenalidomide alone as follows (each cycle will be 28 days in duration with a total of 36 cycles, the planned maximum duration of treatment; every effort should be made to keep patients on the planned dosing schedule):

Daratumumab 1800 mg administered by SC injection:

- Weekly during C1 and C2,
- Every 2 weeks during C3 to C6, and
- Every 4 weeks from C7 onwards until confirmed PD, unacceptable toxicity, or until end of study treatment.

Lenalidomide 10 mg PO:

- D1 to D28 (continuously) of each 28-day cycle until confirmed PD, unacceptable toxicity, or until end of study treatment. If a patient experiences toxicity to lenalidomide, dose and/or schedule may be modified per institutional standard.
- After 3 cycles of maintenance therapy, if well tolerated, the lenalidomide dose may be increased to 15 mg daily, at the discretion of the investigator.

The start of each cycle may occur ± 3 days of the scheduled day to accommodate the schedule of the site or patient. Day 1 of subsequent cycles should be adjusted accordingly to maintain the intended cycle duration. Any delays ≥ 4 days of the scheduled day will need to be discussed with the sponsor.

Daratumumab will be prepared and administered on site, on an out-patient basis, as described in Section 6.2. Guidelines for the prevention and management of daratumumab administration reactions are also described in this section. For further instructions on dose delays due to daratumumab toxicity, please refer to Section 6.3.2.

Lenalidomide will be obtained and administered in accordance with the requirements of the REVLIMID REMS[®] program or the lenalidomide Global Pregnancy Prevention Plan (when lenalidomide is supplied centrally and no local lenalidomide REMS program exists) in Attachment 3. Patients will self-administer lenalidomide and be instructed as follows:

- To swallow capsules whole with water once a day; preferably at the same time each day. Lenalidomide may be taken with or without food.
- To **not** open, break, or chew capsules.
- To **not** handle capsules any more than needed. If a broken lenalidomide capsule or the medicine inside the capsule is touched, the patient should wash the area of his/her body with soap and water.

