6.2. Daratumumab

6.2.1. Preparation and Administration

Detailed instructions for preparation, administration, and storage of daratumumab will be supplied in study reference materials; please refer to the Commercial Prescribing Instructions for drug preparation and administration. An overview of this information is provided below.

In the SC daratumumab group, daratumumab will be provided as a fixed-dosed (1800 mg), combination drug product containing rHuPH20 drug substance (2000 U/mL) and daratumumab

drug substance (120 mg/mL) in a single vial. Manuals with detailed descriptions for preparation and administration of daratumumab will be supplied to each pharmacy and site.

Daratumumab (1800 mg) will be administered by SC injection by manual push over approximately 3 to 5 minutes in the abdominal SC tissues in left/right locations, alternating between individual doses. The volume of the SC solution will be 15 mL for the 1800 mg dose. Refer to the Site Investigational Product Procedures Manual (SIPPM) for additional guidance on SC administration of daratumumab. All patients will be observed for at least 6 hours after the end of the SC injection during Cycle 1 Day 1 and, if deemed necessary by the investigator, after subsequent injections. Reasons for continued observation on subsequent daratumumab injections may include but are not limited to the following: patients with a higher risk of respiratory complications (eg, patients with mild asthma or patients with COPD who have an FEV1 <80% at screening or developed FEV1 <80% during the study without any medical history), patients with IRR with first injection of study drug, patient with a decreased condition on day of dosing compared to prior dosing day. The dose of daratumumab will remain constant throughout the study.

Cycles	Schedule
Cycles 1 to 2	weekly (total of 8 doses)
Cycles 3 to 6 ^a	every two weeks (total of 8 doses)
Cycle 7 onwards until confirmed disease progression, unacceptable toxicity, or end of study treatment ^b	every four weeks
^a First dose of the every-2-week dosing schedule is gi ^b First dose of the every-4-week dosing schedule is gi	ven at Week 9 ven at Week 25

 Table 2:
 Daratumumab Dosing Schedule

All daratumumab administrations will be in an outpatient setting. Patients will receive preinjection medications and post-injection medications as outlined in Section 6.2.2.1 and Section 6.2.2.2, respectively.

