6.3. Dose Delays and Dose Modifications

Dose modification of 1800 mg SC daratumumab (increase or decrease) is not permitted. Dose delay is recommended as the only method for managing daratumumab-related toxicities. Lenalidomide dose may be reduced, or the treatment schedule may be modified for the management of drug-related toxicities, per the investigator's discretion, according to lenalidomide prescribing guidelines.

Toxicities should be attributed, whenever possible, to a specific study drug so that treatment modifications can be made rationally. If multiple toxicities are attributed to an individual study

drug, dose adjustment (for lenalidomide only) should be made according to the guidelines for the most severe toxicity.

Modifications to the planned dosing regimen (lenalidomide only) should be overseen by medically-qualified study-site personnel (principal or sub-investigator unless an immediate safety risk appears to be present).

Study drug administration must be captured in the source documents and the eCRF.

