6.3.2.2. Daratumumab-related Toxicity Management

Refer to Section 6.2.3 for details on management of daratumumab injection-related reactions.

If any of the following criteria are met and the toxicity is more than expected for lenalidomide or underlying multiple myeloma, daratumumab injection must be held to allow for recovery from toxicity. If attribution is unclear, then daratumumab should be held until recovery from toxicity as noted below.

The criteria for a dose delay are:

- Grade 4 hematologic toxicity, except for Grade 4 lymphopenia
- Grade 3 thrombocytopenia with bleeding
- Febrile neutropenia
- Neutropenia with infection, of any grade
- Grade 3 or higher non-hematologic toxicities with the following exceptions:
 - Grade 3 nausea that responds to antiemetic treatment within 7 days
 - Grade 3 vomiting that responds to antiemetic treatment within 7 days
 - Grade 3 diarrhea that responds to antidiarrheal treatment within 7 days
 - Grade 3 fatigue that was present at baseline or that lasts for <7 days after the last administration of daratumumab
 - Grade 3 asthenia that was present at baseline or that lasts for <7 days after the last administration of daratumumab

Administration of daratumumab may be restarted upon recovery from toxicity to Grade 2 or baseline, with the exception that Grade 2 laryngeal edema or Grade 2 bronchospasm must be fully recovered. Other than on Day 1 of a cycle, if any "within-cycle" daratumumab administration does

not commence within the prespecified window of the scheduled administration date (Table 4), then the dose will be considered a missed dose. Administration may resume at the next planned dosing date.

Daratumumab Dosing Frequency	Dose Missed	Dosing Resumption
Weekly	>3 days	Next planned weekly dosing date
Every 2 weeks	>7 days	Next planned every-2-weeks dosing date
Every 4 weeks	>21 days	Next planned every-4-weeks dosing date

 Table 4:
 Daratumumab-related Toxicity Management

A missed dose will not be made up. Delay of Day 1 drug dosing in any given cycle should not result in a skipped dose but should lead to a delay of the entire cycle instead. A minimum of 4 days between daratumumab doses must be observed.

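### SAP 4.3 builds the relative dose intensity denominator from doses given, not doses scheduled, so omitted doses cancel out of the ratio

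*SAP*

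**What the plan says.** SAP 4.3 (Extent of Exposure) gives the measure as follows: "The relative dose intensity (%) defined as the ratio of total dose actually received and total planned dose". The denominator is then spelled out as "planned dose level times the number of administered injections/medications", with these reference levels: "The planned dose for daratumumab is 1800 mg and 10 mg for lenalidomide per administration".

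The protocol sets the dosing to which this is applied:

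- **Daratumumab.** Protocol 6.3 states: "Dose modification of 1800 mg SC daratumumab (increase or decrease) is not permitted". Section 6.2.1 says the same in other words: "The dose of daratumumab will remain constant throughout the study". On omitted within-cycle doses, section 6.3.2.2 states: "A missed dose will not be made up".
- **Lenalidomide.** Section 6.1 schedules 10 mg on all 28 days of each cycle. It tells patients to skip a dose that is more than 12 hours late, and adds that after three well-tolerated cycles "the lenalidomide dose may be increased to 15 mg daily, at the discretion of the investigator". Section 6.3.3 allows a reduced dose or a 21-of-28-day schedule for toxicity.

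SAP 4.3 also plans dose intensity (total dose divided by number of cycles), the number of daratumumab administrations, cycles received, treatment duration, and counts of subjects with cycle delay, dose delay, skipped doses or adjusted doses.

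**The concern.** The denominator is called planned but counts only what was administered. A measure with this name is normally read as the share of the scheduled treatment that reached the patient. As defined, it cannot register an omitted dose of either drug.

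The trial adds daratumumab to lenalidomide, so a reader of the exposure tables will want to know how much of each drug was delivered, and whether lenalidomide delivery differed between arms. The protocol's introduction cites Grade 3 or 4 neutropenia of 50.0% versus 35.3% with and without daratumumab in the MAIA trial, and Table 3 sets a neutrophil threshold for starting each cycle. More omitted lenalidomide in the combination arm is therefore plausible. An RDI table reading about 100% for daratumumab would look like near-complete delivery whatever had happened.

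**Working it through.** The documents state no RDI value, so there is no figure to reproduce. The check is the formula itself plus illustrative patients.

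**Scheduled daratumumab doses** (Protocol 6.2.1, Table 2; 36 cycles from 6.1):

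- Cycles 1–2: 2 × 4 = 8. Cycles 3–6: 4 × 2 = 8. Both match Table 2.
- Cycles 7–12: 6, so 8 + 8 + 6 = 22 through Cycle 12.
- Cycles 7–36: 30, so 8 + 8 + 30 = 46 through Cycle 36.

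**Daratumumab, SAP formula.** For k full injections, RDI = (1800 × k) / (1800 × k) = 100%, whatever number was scheduled.

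**How many doses can be omitted.** Sections 6.3.1 and 6.3.2.2 treat a late Day 1 as a cycle delay, not a skipped dose. The doses that can be skipped are thus the non-Day-1 doses: 2 × 3 = 6 in Cycles 1–2 and 4 × 1 = 4 in Cycles 3–6. Three consecutive missed doses lead to withdrawal from treatment unless the sponsor agrees otherwise (6.3.1, 6.3.2.3, 10.2.1). That leaves at most 2 skips in each of Cycles 1 and 2, so 4 + 4 = 8 in all. The fewest doses compatible with these rules are 22 − 8 = 14 through Cycle 12 and 46 − 8 = 38 through Cycle 36.

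**Lenalidomide, SAP formula.** RDI = total mg / (10 × days taken), which is the mean mg per dose taken divided by 10 mg. The schedule-based version is total mg / (10 × 28 × cycles).

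| Patient | SAP RDI | By schedule |
|---|---|---|
| Daratumumab, 14 of 22 doses | 100% | 14/22 = 64% |
| Daratumumab, 38 of 46 doses | 100% | 38/46 = 83% |
| Lenalidomide 10 mg, 21 of 28 days | 100% | 210/280 = 75% |
| Lenalidomide 10 mg, 14 of 28 days | 100% | 140/280 = 50% |
| Lenalidomide 5 mg, 28 of 28 days | 50% | 140/280 = 50% |
| Lenalidomide 5 mg, 21 of 28 days | 50% | 105/280 = 37.5% |

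The formula responds to a lower mg per dose but not to omitted days.

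**Partial injection.** One half-delivered injection among 46 gives (45 × 1800 + 900) / (46 × 1800) = 98.9%.

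**Does dose intensity per cycle fill the gap?** Partly.

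- Lenalidomide at 10 mg falls from 280 to 210 mg per cycle on 21 of 28 days. At 15 mg on 21 days it is 315, above the 280 of complete 10 mg dosing.
- Daratumumab mg per cycle depends on treatment duration because dosing becomes less frequent. A patient given 16 of 22 doses over 12 cycles (73%) has 16 × 1800 / 12 = 2400 mg per cycle. Complete delivery over 36 cycles has 46 × 1800 / 36 = 2300.

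**The case against.** The best defence is that SAP 4.3 does not rely on RDI alone. Dose intensity per cycle does fall when lenalidomide days are omitted. Lenalidomide has the same starting dose and cycle length in both arms, so mg per cycle can be compared directly. Subjects with delayed, skipped or adjusted doses are counted, SAP 4.2 reports lenalidomide discontinuation with reasons, and SAP 6.1 tabulates adverse events leading to lenalidomide modification or interruption. This stands. A reader might infer that the plan cannot show reduced lenalidomide delivery at all; the documents do not support that, and the SAP never assigns that task to RDI. What remains is that none of these summaries gives a ratio to schedule. Daratumumab mg per cycle shifts with duration, escalation can offset omitted days, and a subject count treats one skipped dose like many.

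Three other inferences also go too far:

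- *Daratumumab RDI must always be exactly 100%.* Protocol 6.2.3.2 allows an injection to be stopped for a reaction, with restart at the investigator's discretion, so partial delivery can lower it.
- *Half the scheduled daratumumab could go missing unseen, say 11 of 22.* The Day 1 rule implies at least 12 doses in 12 started cycles. Table 4 does carry a missed-dose row for every-4-weeks dosing, which sits uneasily with that rule; the two passages should be reconciled, and the argument here does not use that row.
- *A lenalidomide RDI of 150% is an error.* It is the correct ratio of a permitted 15 mg to the 10 mg reference, and a schedule-based denominator gives the same figure for daily 15 mg.

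**Conclusion.** The point holds for RDI and for omitted doses. As written, the statistic is the mean dose per administration relative to the planned level, not the share of scheduled treatment delivered. Within the protocol's own rules, the overstatement for daratumumab reaches 36 percentage points through Cycle 12 (100% against 64%) and 17 points over 36 cycles (100% against 83%). For lenalidomide on 21 of 28 days it is 25 points.

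These are illustrative patients, not predicted averages. They assume fully delivered injections and, for daratumumab, adherence to the Day 1 rule and the limit on consecutive missed doses. This is a descriptive exposure measure: the primary endpoint, PFS, alpha and power are unaffected. It is still worth correcting, because the reported figure would be wrong for what its name says.

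**What to change.** In SAP 4.3, define total planned dose as the planned dose level times the number of administrations the protocol schedules in the cycles the patient started, up to discontinuation of that drug. If the present ratio is wanted, keep it under the name *mean dose per administration relative to planned*.

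Add a sentence saying that the revised RDI captures omitted doses and not calendar time lost to cycle delays, which stay in the delay summaries. Showing lenalidomide patients escalated to 15 mg separately is optional.

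The cost is SAP wording and programming. Protocol section 7 already has each daratumumab administration recorded in the eCRF and lenalidomide intake recorded by diary for the exposure pages, so no new data are needed and no dosing rule changes.
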